Early Activation of Artificial Urinary Sphincter: A Pilot study

Abstract:

Urinary incontinence or loss of bladder control is a troublesome issue for all affected patients. The causes of urinary incontinence and its treatment options vary widely. A commonly encountered reason for urinary incontinence in men is related to treatment for prostate cancer. These treatment options can range from surgical removal of the prostate, external beam radiation therapy, and/or brachytherapy, the insertion of radioactive implants directly into the tissue. Mild cases of incontinence are responsive to more conservative measures, but moderate to severe cases often require placement of an artificial urinary sphincter. Typically, these devices are left deactivated for a period of 4- 6 weeks following implantation to allow swelling to subside before use. We hypothesize that the device could be activated within an earlier timeframe without increasing the risk of complications. No studies to date have evaluated this; therefore we plan to conduct a prospective study in which we will activate the device 3 weeks after placement and monitor for complications.

Aim of the study:

To assess the safety and feasibility of early activation of an artificial urinary sphincter and assess whether or not this increases the risk of postoperative complications. We hypothesize that a period of 3 weeks should allow adequate time for the resolution of urethral and scrotal swelling following artificial urinary sphincter placement, and that activation of the device at that time, as opposed to traditional 4-6 weeks post-operatively, will lead to improved patient satisfaction with no increase in postoperative complications.

Background:

Urinary incontinence is one of the most common complications following surgical treatment of prostate cancer via radical prostatectomy. All patients will have this to some degree in the initial post-operative period, but it typically resolves over time as the newly created urethrovesical anastomosis heals. Wolin et. al reported a 59% rate of urinary incontinence at 6 weeks post-prostatectomy among studied patients¹. For the unfortunate patients who have persistent incontinence requiring the use of multiple pads per day in the absence of a bladder neck contracture or stricture, an artificial urinary sphincter (AUS) may be the best option to regain continence.

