The AUS was first introduced into practice in 1972 at the Baylor College of Medicine. Since that time, it has been found to effectively improve the quality of life of patients with post-prostatectomy urinary incontinence. In a recent analysis, 79% of patients report being satisfied and using no more than one pad per day². The device has undergone numerous revisions since its introduction and the current model, the American Medical Systems (AMS) 800, is widely implanted throughout the U.S. and worldwide. Several studies have been performed validating the AUS as a surgical treatment of post prostatectomy incontinence. There have been varying degrees of success documented in the literature secondary to the different definitions of success used, however, using the definition of zero to 1 pad per day, success rates have varied between 60% and 90% in modern series(3). The most common

complication is urinary retention, which can be managed with a urethral catheter. Less common complications include infection, device malfunction, and urethral erosion³.

The device (see figure 1) is placed in the operating room under general anesthesia. The device consists of a urethral cuff, pressure regulating balloon, and an activation pump and once activated, the urethral cuff will be closed at rest. The patient will squeeze the scrotal pump to open the cuff in order to void once the need arises. Patients are typically discharged the same day without a Foley catheter, unless unable to void in the recovery room. The device is typically left in the de-activated position to allow reductions in urethral edema and scrotal edema before the patient is allowed to manipulate the device. The device is routinely activated at 4-6 weeks post-operatively⁴. A literature review did not reveal any papers or guidelines that show that this period of de-activation of 4-6 weeks is actually required, though Baylor College of Medicine reports current practice of only waiting 4 weeks until activation⁵. There have not been any studies conducted indicating any negative consequences of activating the device early and there have been two or three patients at CAMC who have activated their device a few days post discharge from the hospital, against our advice.. These patients did not report any adverse events with early activation.

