Any patient who has previously undergone artificial urinary sphincter placement and presents for revision or additional cuff placement.

Any patient who is undergoing combined artificial urinary sphincter and inflatable penile prosthesis placement.

Any patient who is a poor candidate for early activation due to poor condition at presentation or signs of infection.

Procedures and Protocol:

There isn't a comparison group for this study; therefore all patients agreeing to participate will have the urinary sphincter activated 3 weeks after surgery. If there are patients that later choose not to have early activation or are found to be poor candidates for three week activation based upon their post op

exam, we will proceed with activation at a 4-6 week time period. While there is no comparison group in the study, patient satisfaction and adverse events for study patients will be compared to historical literature.

Currently patients are not routinely seen for a 3 week follow up appointment, so approximately \$3000 will be requested from Research appropriations to cover the costs of this study. All other costs are standard of care, so patient will be responsible for those costs whether they agree to enroll in the study or not. The money from the CAMC Research Appropriations will be used to cover all the clinical fees for the 3 week visit to activate the AUS.

Pre-procedure:

- 1. All eligible patients will be informed about the study at their regularly scheduled pre-operative office visit. If the patient agrees to participate, they will be consented with the consent form as written. A note is made in the progress note of the patient's chart detailing the consent.
- Original signed consent will be kept and stored in the consent binder at [name] office and one copy of the consent will be placed in the medical record and another will be given to the participant.
- 3. Patient will complete an SF-8 quality of life survey and Incontinence Impact Questionnaire (Appendix A).

Intraoperative procedures:

1. Once consented, the patient will undergo the procedure without any changes to our normal routine. The patient's device will be deactivated at the conclusion of the procedure.

Post-procedure:

- 1. The patient will be discharged post-operatively (same day) and follow-up will be arranged in 3 weeks to activate the device.

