- 2. Study patients have a follow up office visit at 3 weeks (up to 3 weeks and 3 days after the procedure) which includes a post-operative evaluation of their incisions, degree of bruising, tissue induration, tenderness and accessibility of the pump. If these factors are acceptable and pump mechanics are normal, the artificial sphincter will be activated and the patient will be educated on its proper use.
- 3. Additional follow up will include the regular 6 week visit, a visit at 3 months, and then every 6 months for a total of 1 year unless issues arise that necessitates deviation. At each visit, patients will complete the Incontinence Impact Questionnaire and the SF-8 quality of life survey.

Study Chart:

INFORMATION	PRE-	Intra-	POST-Treatment	POST-	POST-	POST-	POST-Operative
	Treat	operative	3 weeks	OperativeTrea	Operative	Operative	Treatment 1 year
	ment	Treatment	(up to 3 weeks and	tment	Treatment 3	Treatment	(+ 1 month)
			3 days after	6 weeks	months	Six months	
			procedure)	(+ 1 week)	(+ 2 weeks)	(+ 3 weeks)	
Inform Subject	Х						
Consent Subject	Х						
Note in Record	Х						
Office visit	Х		Х	X	Х	Х	Х
SF-8 survey administered	Х			Х	Х	Х	Х
Incontinence Impact Questionnaire	Х		Х	Х	х	Х	Х
Procedure conducted		Х					
Data Collection	Х	X	Х	Х	Х	Х	Х

Data Collection and Management:

The SF-8 is a quality of life instrument related to health functioning that provides an eight question brief assessment of physical and mental health⁶. It has been found to have adequate reliability and validity in prior studies for quality of patient life and it incorporates a manual for easy interpretation.⁷. The Incontinence Impact Questionnaire short form was adapted from a survey that was developed for women with stress incontinence. This questionnaire has been validated for use in men after radical prostatectomies and consists of 7 items in which measures the effect of Urinary Incontinence on quality of life⁸.

Following surgery, patient characteristics and operative details will be recorded. These will include:

- Medical Record Number
- Patient name
- Age
- BMI
- Operative time
- Artificial sphincter cuff size
- Pressure-regulating balloon size
- Intra-operative complications (urethral injury, bleeding)
- Reason for AUS placement (Post-prostatectomy, Radiation therapy for prostate cancer, or Incontinence related to TURP)
- Finish date of prostate cancer treatment or TURP
- Preoperative daily pad usage
- Pre-surgery SF-8 survey

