- History of medication
- Date device is activated
- Comorbidities
- ECOG Score

- ASA Score
- Tobacco Use
- Diabetes

When the study patient follows up at 3 weeks postoperatively, we will assess for immediate postoperative complications:

- Post-operative urinary retention Y/N
- Bleeding Y/N
- Presence/concern for infection Y/N
- Presence/concern for urethral erosion Y/N

When any patient follows up at 6 weeks, 6 months, and 12 months postoperatively, we will assess:

- Postoperative daily pad usage
- Perceived improvement in incontinence (scale 1 (none) 10 (very satisfied))
- Presence/concern for infection Y/N
- Presence/concern for urethral erosion Y/N
- Post-surgery SF-8 surveys (6 weeks, 3 months, 6 months)

Statistical Analysis:

The Center of Health Service and Outcomes Research will conduct the data analysis. For this exploratory study, selection of appropriate statistical measure will be determined by CAMC Center for Health Education and Research Institute. Specific tests will be determined by whether the data is continuous or categorical. Descriptive statistics will be used as appropriate and comparisons will be done using student's T-test and chi-square test. In addition univariate and multivariate multiple logistic regressions will be used to determine which variables predict patient's outcomes. All comparisons will be done at 95% of level of significance.

I. Human Subjects

Study population: All patients undergoing artificial urinary sphincter (AUS) placement by a single surgeon, [name] at Charleston Area Medical Center.

Recruitment methods: All patients, following informed consent, that meet the inclusion criteria are eligible to participate in the study. Patients will be consented by the principal investigator only at time of usual surgical informed consent using the attached consent form. Consent will be obtained prior to the surgical procedure.

Benefits: Early activation of the artificial urinary sphincter will allow the patient to regain continence earlier.

Risks and discomforts: The principle risks of participation in this study will be the standard risks of the operation.

Less often, there are risks of bleeding, infection, urinary tract injury, device erosion, wasting away of muscle mass in the urinary tract, or loss of bladder control.

Occasionally, there are risks of persistent loss of bladder control or mechanical failure of device.

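### The only item that mentions satisfaction mixes it with improvement, and the plan does not define who counts as satisfied

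*Combined protocol and SAP*

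**What the plan says.** The hypothesis under Aim of the study has two parts: earlier activation "will lead to improved patient satisfaction with no increase in postoperative complications". There is no control group. Procedures and Protocol states instead that "patient satisfaction and adverse events for study patients will be compared to historical literature".

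The outcome list under Data Collection and Management opens with "When any patient follows up at 6 weeks, 6 months, and 12 months postoperatively, we will assess" and includes one line that touches satisfaction: "Perceived improvement in incontinence (scale 1 (none) 10 (very satisfied". Daily pad use is a separate line in the same list.

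Two questionnaires are also used. The SF-8 "provides an eight question brief assessment of physical and mental health". The Incontinence Impact Questionnaire (IIQ-7) "consists of 7 items in which measures the effect of Urinary Incontinence on quality of life".

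Background gives one published figure that involves satisfaction: "79% of patients report being satisfied and using no more than one pad per day". It also gives a range for continence alone: "using the definition of zero to 1 pad per day, success rates have varied between 60% and 90% in modern series".

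Statistical Analysis names t-tests, chi-square tests and logistic regression. It sets no cut-off or scoring rule for the 1-10 item.

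**The concern.** A rating scale can be interpreted when both ends describe more or less of the same thing. Here 1 means no improvement and 10 means high satisfaction. A man who is much drier but unhappy with the device has no clear place on that scale, and neither has a man who has improved little but is content. A score of 5 could reflect moderate improvement, moderate satisfaction or a disagreement between the two. Once the answers are in, nothing in the data set can tell these apart.

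The second gap would remain even if the anchors were perfect. A 1-10 score becomes a proportion only through a cut-off, and the plan has none. The choice would then be made after the scores are seen, with the published figure already known.

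At stake is the satisfaction half of the hypothesis. The safety half does not depend on this item.

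**Working it through.** The plan states no figure for this outcome and did no power calculation, so there is nothing to reproduce. The check is textual, followed by two illustrations.

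**Step 1: does anything else measure satisfaction?** Appendix A prints both questionnaires.
- SF-8: overall health, physical limitation, daily work, pain, energy, social activity, emotional problems and usual activities. No satisfaction question.
- IIQ-7: chores, recreation, entertainment, travel, social activity, emotional health and frustration, all as affected by leakage. Frustration comes closest, but it is not satisfaction with the device or the result.
- Pad use: continence.

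The 1-10 item therefore stands alone.

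**Step 2: what does the item measure?**
- Stem: improvement.
- Value 1: *none*, which completes the improvement stem.
- Value 10: *very satisfied*, which does not.

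A dash or connecting word may have been lost between the two anchors when the PDF was read. That would not change either anchor.

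**Step 3: how many scores?** 25 men (enrolment target) × 3 listed visits = 75. This is a ceiling that assumes full enrolment and full attendance. It is a count, not an effect size.

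**Step 4: does the missing cut-off matter?** Assume a normal score with mean m and SD 2, rounded to whole points. These values are assumptions, not taken from the document. The share scoring c or more is 1 − Φ((c − 0.5 − m)/2). For m = 7.5 and c = 6 this is 1 − Φ(−1) = 0.84.

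| Cut-off c | m = 7 | m = 7.5 | m = 8 |
|---|---|---|---|
| 6 | 77% | 84% | 89% |
| 7 | 60% | 69% | 77% |
| 8 | 40% | 50% | 60% |
| 9 | 23% | 31% | 40% |

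With m = 7.5 or 8, the same scores fall above 79% at a cut-off of 6 and below it at 7 or higher.

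**Step 5: what could a proportion show at n = 25?** Exact (Clopper-Pearson) 95% limits for x satisfied are the 0.025 quantile of Beta(x, 25 − x + 1) and the 0.975 quantile of Beta(x + 1, 25 − x).
- x = 20 (80%): 59% to 93%.
- x = 23 (92%): 74% to 99%, which still includes 79%.
- x = 24 (96%): lower limit 79.6%, the smallest count whose interval lies above 79%. P(X ≥ 24) when the true proportion is 0.79 is 0.021.
- x = 15 (60%): upper limit 78.9%, the largest count whose interval lies below 79%.

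This treats 79% as fixed and known.

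**The case against.** The strongest reply is that this is a small, single-arm, exploratory pilot whose stated aim is safety and feasibility, and whose abstract frames the hypothesis around complications only. Step 5 shows that a well-worded item would still give a wide interval. Without a control group, it would say little about 3 weeks against 4-6 weeks. That stands, and it limits what the comparison can deliver. It does not remove the defect, because the protocol itself commits to the satisfaction hypothesis and to the comparison.

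The entry may also be shorthand. It sits in a list of data elements, and Appendix A does not print the wording patients will see. That is possible, but the list is the only definition given, and a form built from it would carry the mismatch.

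Four stronger readings are tempting and are not supported:
- A reader might infer that the item measures neither construct. The stem does ask about improvement, and the score can be read loosely as satisfaction with improvement. It mixes the two.
- A reader might infer that the mixed anchors are what prevent comparison with a percentage. The missing cut-off does that, and any 1-10 score yields a proportion once a cut-off is set.
- A reader might take 79% as the planned comparator. It appears only in Background, and the plan refers only to historical literature. Other sources may use numeric scales; this cannot be checked here.
- A reader might infer that no comparison is possible. Pad use is collected, so the 60% to 90% range for zero to one pad per day remains usable.

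**Conclusion.** The point holds in two separate parts. First, the sole item bearing on satisfaction changes construct between its ends, so its score cannot be assigned to improvement or to satisfaction and cannot be repaired at analysis. Second, no definition of *satisfied* is pre-specified, so the score has no agreed match to the one satisfaction figure in the document.

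The reach is up to 75 scores and the satisfaction part of the hypothesis. Complications, pad use, SF-8 and IIQ-7 are unaffected. The direction and size of any bias cannot be derived, because the document does not show how often improvement and satisfaction would diverge. The cut-off illustration depends on the assumed means and SD; the exact intervals depend only on n = 25 and on taking 79% as fixed. The change is worth making before further data are collected, because the protocol commits to this outcome and the correction is small.

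**What to change.** Replace the single entry with:
1. Perceived improvement in incontinence, 1 = none to 10 = complete.
2. Satisfaction with the device, 1 = very dissatisfied to 10 = very satisfied.
3. A yes/no question asking whether the patient is satisfied. Alternatively, omit this and pre-specify a cut-off on item 2.

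Print the exact wording in Appendix A. In Statistical Analysis, name the historical comparator and its definition of *satisfied* before the data are examined, and report the matching proportion with an exact 95% CI. If the 79% figure is chosen, the matching quantity is satisfied and using at most one pad per day, provided the source confirms that 79% is a joint proportion.

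Describe the comparison as descriptive. The interval is wide at 25 patients. The title of the series cited for 79% also describes it as long-term and as including secondary implantations, whereas this study excludes men with a previous device and follows patients for one year.

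The cost is two net lines on the follow-up form and a short protocol wording change, with no new visit. Any scores already collected on the present wording should be reported separately rather than merged with the new items.

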When inflated, the cuff constricts the urethra and blocks the passage of any urine. When deflated, the cuff reduces pressure on the urethra and allows for the free passage of urine.

[figure not shown]

Figure 5 AUS with Foley catheter

A foley catheter is also inserted during surgery, which is removed prior to discharge from the hospital. The artificial sphincter cuff is not inflated immediately after surgery, in order to allow the tissues to heal.

Significance:

Post-prostatectomy urinary incontinence is a troubling complication following treatment (radical prostatectomy, radiation therapy, or brachytherapy) for prostate cancer, or in rare instances the treatment of benign prostatic hypertrophy, and significantly decreases quality of life in affected patients. An artificial urinary sphincter has been found to significantly improve quality of life in these patients. Providing data which demonstrates the safety and feasibility to activate an artificial urinary sphincter 3 weeks after surgery as opposed to 4-6 weeks will allow men to regain their continence earlier, therefore improve their quality of life.

Methods

Study Design:

The design will be a single institute prospective study with patients undergoing artificial urinary sphincter placement by the operating surgeon, [name] at Charleston Area Medical Center in Charleston, WV. All patients following informed consent that meet the inclusion criteria are eligible to participate in the study.

Sample:

All male patients with moderate to severe urinary incontinence who have been treated for prostate cancer (radical prostatectomy, External Beam Radiation therapy or brachytherapy, or Incontinence related to trans urethral resection of the prostate (TURP) or simple prostatectomy undergoing artificial urinary sphincter placement at Charleston Area Medical Center by [name], D.O. will be offered the chance to participate in this study. This is a pilot study and thus no power analysis to calculate necessary sample size is conducted to determine a number that would yield sufficient power. We will aim to enroll 25 patients, which we anticipate to be accrued within 3 years from the start of the study. We will have 1 study group: those who are activated at 3 weeks post implantation.

Inclusion Criteria:

All patients undergoing artificial urinary sphincter (AUS) placement by a single surgeon, [name].

Exclusion Criteria:

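### Chi-square is the only named comparison test that fits the yes/no complications, and with 25 men it is unreliable at low rates; exact methods should be named instead

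*Combined protocol and SAP*

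**What the plan says.** The Sample section plans a single arm: "We will have 1 study group: those who are activated at 3 weeks post implantation". On size it says "We will aim to enroll 25 patients, which we anticipate to be accrued within 3 years from the start of the study", and that "This is a pilot study and thus no power analysis to calculate necessary sample size is conducted". Procedures and Protocol supplies the comparator: "patient satisfaction and adverse events for study patients will be compared to historical literature". It gives no historical rate and no series size.

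Data Collection and Management records retention, bleeding, infection and erosion as yes/no at the 3-week visit, and infection and erosion again at later visits.

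The Statistical Analysis section calls the study exploratory and says that "selection of appropriate statistical measure will be determined by CAMC Center for Health Education and Research Institute". It goes on: "Specific tests will be determined by whether the data is continuous or categorical". The next sentence provides for descriptive statistics and then says that "comparisons will be done using student's T-test and chi-square test". Logistic regression is named separately, for finding predictors. Comparisons are set at a 95% level, with no sidedness stated. No exact test, small-cell rule or confidence interval for a complication proportion is mentioned.

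On frequency, Background says only: "Less common complications include infection, device malfunction, and urethral erosion". It describes retention as the most common complication, also without a figure.

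**The concern.** The study's aim includes judging whether activation at 3 weeks raises the risk of complications. If the analyst follows the named tests, that judgement comes from a chi-square on a handful of events. Chi-square relies on a large-sample approximation that is usually trusted only when expected counts reach about 5. With 25 men and uncommon events they do not.

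The likely error is a false alarm. The distribution of events is skewed, so almost all of the test's error falls on the side of an apparent increase. Two or three events that are compatible with chance could be published as a significant excess of harm from early activation.

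**Working it through.** The plan states no error rate or power for this comparison, so there is no figure to reproduce. The check asks how an uncorrected chi-square behaves with 25 men.

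**Inputs**
- n = 25, from the Sample section.
- Yes/no outcomes, from Data Collection and Management.
- Comparison with the literature, from Procedures and Protocol.
- Assumption: two-sided 5%, so 2.5% per tail and a cutoff of 3.841. The plan gives only the 95% level.
- Assumption: a fixed reference rate p0, scanned from 1% to 13%. The documents give no rate.

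**Step 1: expected count.** It is 25 × p0, which reaches 5 only at p0 = 5/25 = 20%. At 2%, 4% and 10% it is 0.5, 1.0 and 2.5.

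**Step 2: false declaration of an increase.** For k events the statistic is (k − 25·p0)² / (25·p0·(1 − p0)). The test rejects above 3.841. The true error is the Binomial(25, p0) probability of the counts above expectation that reject. For comparison, the exact binomial test rejects at the smallest count whose upper tail is 2.5% or less.

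| p0 (assumed) | Chi-square calls an increase at | True error | With Yates correction | Exact binomial test |
|---|---|---|---|---|
| 2% | 2 or more | 8.9% | 1.3% (3 or more) | 1.3% (3 or more) |
| 4% | 3 or more | 7.6% | 1.7% (4 or more) | 1.7% (4 or more) |
| 5% | 4 or more | 3.4% | 3.4% (4 or more) | 0.7% (5 or more) |
| 10% | 6 or more | 3.3% | 3.3% (6 or more) | 0.9% (7 or more) |

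Over 1% to 13%, in steps of 0.01 percentage points:
- Uncorrected chi-square: minimum 1.8%, maximum 10.6% (near p0 = 2.2%), mean 4.1%. The error is not monotone in p0. It is 2.4% at 2.5% and 2.1% at 9%, both under the intended tail.
- Yates correction: maximum about 4.7%.
- Exact binomial test: about 0.2% to 2.5%.

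**Step 3: worked example, 3 of 25 against 4%.** The expected count is 25 × 0.04 = 1 and the variance is 25 × 0.04 × 0.96 = 0.96. Chi-square = (3 − 1)²/0.96 = 4.17, p = 0.041. The exact probability of 3 or more events is 1 − (0.360 + 0.375 + 0.188), which is 0.076 from unrounded terms. Chi-square reports significance where the exact upper tail is three times 2.5%.

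Similarly, 2 of 25 against 2% gives (2 − 0.5)²/0.49 = 4.59, p = 0.032. The exact upper tail is 0.089.

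**Step 4: comparison with a published cohort (2×2 table, assumed cohort sizes).** With 100 historical men the upper-tail error is 9.1% at a 1% rate and 8.1% at 2%. With 200 to 1,000 men and rates of 1% to 10% it is 3.4% to 6.2%. The inflation shrinks but does not disappear.

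**Step 5: decreases.** Zero events gives chi-square = 25·p0/(1 − p0), which passes 3.841 only once p0 exceeds 3.841/28.841 = 13.3%. For the exact test, (1 − p0)^25 must be 0.025 or less, so p0 must be at least 1 − 0.025^(1/25) = 13.7%. Neither test can call a decrease below about 13% to 14%.

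**The case against.** The plan does not prescribe chi-square for complications. It names the t-test and chi-square generically, calls the study exploratory, allows descriptive statistics, and leaves the choice of measure to the institute. An exact test, or a Yates correction, is open to the analyst. This stands, and it limits the severity. Open discretion with no small-cell rule does not, however, commit anyone to a suitable method, and chi-square is the only named comparison test for this type of outcome.

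The error rates rest on assumed reference rates, an assumed two-sided level and a fixed comparator. That stands too. The size of the inflation depends on which rate is taken from the literature, and at some rates there is none.

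The study is a pilot with no power analysis, and no formal decision rule hangs on these p-values. The error is a false alarm, not a missed harm, and exact tests make a real increase harder to declare. All of this is fair. It makes the point minor and makes the interval more useful than the test.

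A reader might also infer that chi-square is at fault for being unable to show a decrease. The documents do not support that as a criticism of the test. The limit comes from having 25 men, the exact test shares it, and the stated hypothesis is that complications do not increase.

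**Conclusion.** The point holds as a minor one. With 25 men, expected counts are below 5 for any rate under 20%. For assumed fixed reference rates of 1% to 13%, the uncorrected chi-square's chance of falsely declaring an increase is 1.8% to 10.6%, with mean 4.1%, against 2.5% per tail. With Yates correction it is at most about 4.7%. These figures depend on a two-sided 5% level and on chi-square actually being used, neither of which the plan states.

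A reader might infer that the error is four times nominal. That describes only the peak near a 2.2% rate, measured against one tail (10.6/2.5 = 4.2). Against the full 5% it is 10.6/5 = 2.1 times, and the mean over the range is 4.1/2.5 = 1.6 times the tail. With no complication rate in the documents, the peak cannot be presented as the expected case.

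**What to change.** Add to the Statistical Analysis section:

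> Complication proportions will be reported with exact (Clopper-Pearson) 95% confidence intervals. Any comparison with a fixed published rate will use the exact binomial test, and any comparison with a published cohort with known counts will use Fisher's exact test. Chi-square will not be used where any expected count is below 5.

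This changes nothing in the design, sample size or conduct. Its price is conservatism: the exact binomial test attains only about 0.2% to 2.5% in the upper tail at these rates, so a true increase needs more events to be declared (4 rather than 3 against a 4% rate). It does not restore the ability to show a decrease, but the interval makes that limit visible: zero events in 25 has an upper bound of 13.7%.
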